Vaccine-hesitant parents (VHPs) are an important population for targeted interventions aimed at improving vaccine acceptance.²⁷ VHPs are a large (10-30%),^{13,17,18,28,29} heterogeneous group of parents who refuse and/or delay at least one recommended vaccine for their child.³⁰ Compared to the small minority (1-2%) of parents who completely reject vaccines,³¹ VHPs hold less negative attitudes and beliefs towards vaccines^{13,30,32-34} and therefore are more likely amenable to behavior change.²⁷

Provider communication with VHPs is critical to achieving this behavior change.³⁵ VHPs consider their child's pediatric provider to be a key information source in their decision-making about vaccines and their child's health,^{13,15,30,32,36} with a proportion of initially hesitant parents reporting that they changed their mind about delaying or refusing a vaccine after their child's provider addressed their concerns, provided them with additional information, or gave them reassurance.^{13,15} **Consequently, how providers discuss and recommend vaccines is significant.** The quality and presence of a provider's recommendation has been associated with increased uptake of childhood and adolescent vaccines.³⁷

⁴⁷ [ENREF 37](#) [ENREF 41](#) [ENREF 44](#) [ENREF 45](#) Moreover, [name] et al. have found in observational work that the communication format used to initiate the vaccine recommendation is influential: a presumptive (e.g. *"Well we have to do some shots."*) rather than a participatory (e.g. *"How do you feel about vaccines today?"*) format was associated with increased parental vaccine acceptance of childhood vaccines.^{14,16} [ENREF 42](#) In a recent randomized controlled trial (RCT) based on this work, there was a 5.4% (95% confidence interval [CI]: 1.1%-9.7%) increase in HPV vaccine uptake in adolescents attending clinics whose providers received training on the presumptive format for initiating the HPV vaccine recommendation compared to control clinics whose providers received no training, with no difference in uptake between control clinics and clinics whose providers received training on use of the participatory format.⁴⁸ [ENREF 49](#) This evidence strongly suggests that provider use of the presumptive format can increase parental acceptance of vaccines.

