C.1.b. Impact of a Provider Communication Strategy on Parental Vaccine Hesitancy Towards Childhood Vaccines ([name], Co-I): [name] et al. conducted a cluster RCT of 56 pediatric and family medicine clinics in the greater Seattle metropolitan area to test the effect of a provider communication strategy on parental vaccine hesitancy.²⁸ There were 26 clinics in the control arm in which parents of newborns received usual care and 30 clinics in the intervention arm in which providers received training on a communication strategy called: "Ask, Acknowledge, and Advise." The centerpiece of this strategy was an algorithm in which providers were first encouraged to begin the vaccine recommendation by asking parents what questions they had about the immunization schedule, then acknowledging parental vaccine concerns, and finally, advising parents in a manner specific to their concerns. The intervention training included a well-attended (68% of providers) didactic session at baseline that incorporated videos of providers modeling the communication strategy. Providers in intervention clinics also received paper materials detailing the framework as well as monthly e-mail newsletters and a link to the study website that included a webinar version of the training.

Our primary outcome was the change in the proportion of parents who were VHPs (as measured by the PACV) at recruitment after the birth of their child and follow-up when the child was 6 months old. We found that among all enrolled parents, 11.3% were VHPs. The proportion of VHPs at baseline and follow-up changed

Table 1. PACV-SF: Positive if ≥ 2 hesitant responses

No.	Item	Hesitant Response
1	Have you ever delayed having your child get a shot for reasons other than illness or allergy?*	Yes
2	How concerned are you that a shot might not prevent the disease?	Very concerned, somewhat concerned, or not sure
3	Overall, how hesitant about childhood shots would you consider yourself to be?	Very hesitant, somewhat hesitant, or not sure
4	I trust the information I receive about shots.	Strongly disagree, disagree, or not sure

*Only delay of the birth dose of the hepatitis B vaccine would be relevant for parents of children ≤ 2 months old, as was used and evaluated in a prior study¹⁸

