C.6. Aim 2: To evaluate the impact of the PIVOT with MI intervention on child immunization status at 19 months of age.

C.6.a. Overview and Design: We propose to conduct a cluster RCT (Figure 3). We will randomize PSPRN and COCONet practices (N=24) to control and intervention arms using a covariate-constrained randomization approach. All parents of newborn infants receiving health supervision at a study practice will be screened for vaccine hesitancy at their child's initial visit using the PACV-SF (see C.1.a.) in order to identify VHPs, the primary study population. Providers at intervention practices will receive the proposed 5-component PIVOT with MI provider training program (see C.5.b.). Providers at control clinics will give usual care. A subset of VHPs at intervention clinics who give us permission to contact them will have their child's health supervision visit videotaped to assess intervention fidelity. Our main outcome will be child immunization status at 19 months expressed as the mean percentage of days under-immunized from birth to 19 months.

[figure not shown]
C.6.b. Setting and Population: Two regional PBRNs (PSPRN and COCONet) from 2 states (Washington and Colorado) will serve as the study setting (see C.2.). Both Washington and Colorado are ideal settings to conduct a study of an intervention designed to improve immunization rates among VHPs because both have a high prevalence of VHPs, with each ranking in the highest quintile among US states with respect to the proportion of parents claiming non-medical exemptions for their child from required school-entry vaccines.²

C.6.c. Eligibility: Providers will be eligible if they belong to PSPRN or COCONet. All English- and Spanish-speaking parents with a newborn infant <1 month old receiving health supervision at a participating practice during the intervention period will be eligible. VHPs, defined as those who have a positive PACV-SF (see C.1.a.), will constitute our primary study population because we are most interested in changing their vaccination behavior.^{10,27} VHPs at intervention practices who indicate on the PACV-SF that study staff can contact them about participation in additional study activities will be eligible for the fidelity study (Aim 2a).

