For our fidelity study (Aim 2a), we will use conversation analysis (CA) to analyze use of the presumptive format to initiate the vaccine recommendation in videotaped data and the Motivational Interviewing Treatment Integrity (MITI) 4 system¹¹⁹ to assess MI fidelity. CA is the same analytic technique we have used in our preliminary work (see C.1.c.) and searches for patterns in the provider-parent interaction in which a behavior is systematically used to accomplish a social action either vocally or nonvocally.¹²⁰ MITI utilizes a 5-point Likert type scale to assess four MI dimensions (cultivating change talk, softening sustain talk, partnership, and empathy) and tallies 10 specific practitioner behaviors (questions, reflection, persuade with permission, giving information, affirm, emphasize autonomy, seek collaboration, persuade and confront). Summary scores include: (1) reflection to question ratio, (2) percentage of complex to simple reflections, and (3) percent of MI adherent statements.

[name] will utilize a subset of the videotaped encounters to develop a coding scheme for the PIVOT with MI communication practices. [name] and [name] will teleconference weekly with [name] during this analysis to review identified communication patterns and their correlation to the PIVOT with MI intervention. After completion of the coding scheme, [name] will then train multiple coders from the study team on the coding scheme using 10% of the videotaped data. We will measure inter-rater reliability between the coders using up to an additional 20% of the data until κ scores reach a minimum of .70. Coders will then continue to independently code all remaining data (and recode the initial 10% of training data). All discrepancies in coding between the coders will be resolved through discussion with [name].

C.6.k. Sample Sizes/Power Calculations: Based on preliminary data (see C.1.a.), children of VHPs had a mean percentage of days under-immunized of 26.2% (standard deviation [SD] 29.8) from birth to 19 months of

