age for 6 vaccines combined (Hepatitis B, DTaP, Hib, IPV, MMR, and Varicella).¹⁸ This corresponds to an average of 37 days late per vaccine dose. To be able to detect with adequate power ($\geq 90\%$) a decrease in under-immunization of 10 days—a decrease that has the potential to be clinically meaningful since 27 days would not be considered late for most vaccines because of the 30 day window in which most vaccine doses are recommended¹²¹—we need to enroll 600 VHP/newborn pairs total, with 300 per arm and 25 at each of the 24 study practices (assuming an α of 0.05, a SD of 20, and an intraclass correlation coefficient for within-clinic correlation of 0.02²⁸). Assuming a 10% prevalence of VHPs (see C.1.b),²⁸ we will need to approach 6,000 parents to reach our sample size goal. This is feasible to achieve in our designated 18 month recruitment period given our design to integrate PACV-SF screening of parents of newborns into standard practice workflow and our estimate (determined by spot chart reviews at PSPRN and COCONet practices) that there are ≥ 10 newborns per clinic per week in PSPRN and COCONet practices. If we vary our assumptions regarding VHP prevalence (7.5%) or SD (25), we would need to approach 8,000 and 12,000 parents, respectively, for adequate ($\geq 90\%$) power to detect the same effect size, both of which remain feasible within the 18 month enrollment period assuming ≥ 10 newborns per clinic per week. If we have unbalanced enrollment across study arms (i.e. not 1:1 enrollment in intervention and control arms), we will continue enrollment beyond 600 VHP/newborn pairs total in order to reach at least 300 VHP/newborn pairs per arm given the impact of an imbalance on our power.

For our fidelity outcome (Aim 2a), power can be considered in terms of the number of videotaped interactions needed to develop this coding scheme. Based on our prior studies (see C.1.c.), 3 videotaped visits per provider should be adequate to achieve sufficient behavioral variation across providers. We will therefore videotape up to 360 encounters (up to 180 in each state), which averages to 3 videotaped encounters per practice provider.

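### Strength of hesitancy, already measured at baseline, is not a prespecified covariate in the primary model, although PACV-SF positivity probably takes in some complete vaccine rejecters

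*Combined protocol and SAP*

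**What the plan says.** Section A describes VHPs as a heterogeneous group, 10-30% of parents, who refuse or delay at least one vaccine. It sets them beside complete rejecters ("Compared to the small minority (1-2%) of parents who completely reject vaccines"), says that VHPs hold less negative views "and therefore are more likely amenable to behavior change", and gives this as the reason to target them.

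Section C.6.c turns this into an eligibility rule: "VHPs, defined as those who have a positive PACV-SF (see C.1.a.), will constitute our primary study population". There is no upper limit and no item on complete refusal. Table 1 heads the instrument "Positive if ≥ 2 hesitant responses"; the text of C.1.a gives the cut-off as at least 3 of 4. The items cover past delay, concern that a shot may not work, overall hesitancy and trust.

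Section C.6.g adds demographic items and embeds the PACV-SF in a larger survey. Section C.6.j compares baseline characteristics by arm and adjusts for those found unbalanced. For the primary outcome it names neither the PACV-SF score nor refusal as a covariate, subgroup or sensitivity analysis.

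For the sample size, C.6.k reports that "children of VHPs had a mean percentage of days under-immunized of 26.2% (standard deviation [SD] 29.8", on a six-vaccine form of the outcome, and plans with an SD of 20. "Assuming a 10% prevalence of VHPs", it expects to approach 6,000 parents for 600 pairs.

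**The concern.** A parent who rejects all vaccines would plausibly give hesitant answers to enough Table 1 items to screen positive at either cut-off. Under C.6.i a child with no doses scores 100%. A small group of such children, if present, sits far from the pilot mean of 26.2% and adds much to the outcome variance. If these parents also respond less, as Section A suggests, the average effect in the primary population is diluted.

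The plan collects a graded baseline measure that should carry part of this information, but it would enter the model only if the arms happened to differ on it. Adjusting for a prognostic covariate gains precision whether or not the arms are balanced. Choosing covariates by baseline tests gives up that gain in most realisations and leaves the final model unknown until the data are seen. What is at stake is the width of the primary confidence interval and how the average effect is read.

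**Working it through.** **Inputs.** Rejecters 1-2% of parents and VHPs 10-30% (Section A); planning prevalence 10%, 300 per arm, 24 practices of 25, ICC 0.02, planning SD 20, α 0.05, and 10 days as the target against a mean of 37 days (C.6.k); pilot mean 26.2 and SD 29.8 (C.6.k). Two-sided testing and no dropout are assumed.

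**1. The plan's own figure.** Target = 26.2 × 10/37 = 7.08 points. Design effect = 1 + 24 × 0.02 = 1.48. SE = SD × √(2 × 1.48/300). At SD 20, SE = 1.99 and power is 94.6% (normal) or 92.6% (t, 22 df), so the stated 90% or more reproduces. At SD 29.8, SE = 2.96 and power is 67% or 63%.

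**2. Possible share of rejecters among VHPs.** 1%/30% = 3.3%; 2%/30% = 6.7%; 1%/10% = 10%; 2%/10% = 20%. These assume that all rejecters attend, complete the survey and screen positive.

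**3. Variance supplied.** With share p at mean score L, between-group variance B = [p/(1−p)] × (L − 26.2)², set against 29.8² = 888. For p = 10% and L = 100: 0.1111 × 5446 = 605, or 68%.

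| Share p | L = 100 | L = 90 | L = 80 |
|---|---|---|---|
| 3% | 19% | 14% | 10% |
| 5% | 32% | 24% | 17% |
| 10% | 68% | 51% | 36% |

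At L = 100, B equals all 888 units at p = 14.0%, so a 20% share (minimum SD 36.9) cannot fit the pilot SD. Half the variance needs p of about 7.5%.

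**4. Dilution.** If rejecters do not respond, an average fall of 7.08 needs 7.08/(1−p) among the others, whose mean is (26.2 − pL)/(1−p). At p = 10%, L = 100: 7.87 on 18.0, a 44% relative fall. At p = 3%, L = 80: 7.30 on 24.5, or 30%. The undiluted figure is 7.08/26.2 = 27%.

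**5. Gain from a baseline covariate.** Residual SD = 29.8 × √(1 − R²). R² for the PACV-SF item count is not in the documents. Illustratively, R² of 0.05, 0.10 and 0.20 gives SD 29.0, 28.3 and 26.7, and power for 7.08 points of 65-69%, 67-71% and 73-76% (t and normal), with the ICC held at 0.02.

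For an intention item, let q = p·Se + (1−p)(1−Sp) and φ² = [p(Se − q)]²/[p(1−p)q(1−q)]; residual variance is 888 − φ²B. Assume specificity 97% and L = 100:

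| Share p | Sensitivity | Residual SD | Power, 7.08 points |
|---|---|---|---|
| 10% | 70-90% | 24.7-22.1 | 79-90% |
| 10% | 50% | 26.8 | 72-76% |
| 5% | 70-90% | 28.0-27.1 | 68-75% |
| 3.3% | 50% | 29.3 | 64-68% |

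If rejecters do not respond and the others gain 7.08, the average effect at a 10% share is 6.37, and the first row falls to 70-83%.

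**The case against.** The plan does not contradict itself. A reader might infer that Section A excludes rejecters, or treats them as immovable, and that C.6.c breaks this. Section A is only comparative, and it describes VHPs as heterogeneous. The presumptive format is used with every parent, so all screen-positives are a natural pragmatic population. This objection stands.

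A reader might also infer that rejecters dominate the outcome variance. That needs a share of at least about 7.5% and scores near 100, and the documents establish neither. Survey completion is voluntary, and the pilot mean and SD do not by themselves reveal a cluster at the ceiling: a smooth beta distribution with those moments puts only 0.6% of children above 99. This stands too.

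Nor does chance imbalance in rejecters bias the comparison. At a 10% share scoring 100 (82 points above the others), one SD of imbalance is 82 × √(2 × 0.1 × 0.9 × 1.48/300) = 2.4 points. That is a component of the ordinary standard error of 2.96, already counted in the test and interval. C.6.e also balances practices on percent VHPs and immunization rates, which the 2.4 ignores.

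Finally, the starting power of 63-67% comes from using SD 29.8 instead of 20, which is a separate matter. The larger survey is not reproduced, so it may already hold an intention item.

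None of this answers the remaining point: a baseline measure that is likely prognostic, and costs nothing more to collect, is left to enter the model only by chance imbalance.

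**Conclusion.** The point holds as one of precision and dilution, not of bias or contradiction. The primary population probably includes some complete rejecters, and the primary model does not fix strength of hesitancy as a covariate. Under shares of 3-10% and scores of 80-100, rejecters would supply roughly 10% to 68% of the pilot variance. The upper end needs 10% of VHPs to be rejecters, all scoring 100; a 20% share cannot be reconciled with the pilot SD.

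That rejecters attend, answer and screen positive is inferred from the item content and the missing upper limit. The variance figures carry a six-vaccine pilot over to the eight-vaccine outcome. The power gains depend on predictive strength that the documents do not give, and may be small.

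**What to change.** In C.6.j:

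- Enter the number of hesitant PACV-SF items as a fixed covariate in the primary mixed model, whatever the baseline tests show.
- Keep all PACV-SF positives in the primary intention-to-treat analysis.
- Prespecify a supportive estimate, with confidence interval, of the arm effect by baseline hesitancy level.
- Do not classify rejecters from doses received by 19 months, since that conditions on the outcome.

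This costs analysis-plan wording only and uses data already collected, including for parents already enrolled. Its limit is range: among positives the count runs from 2 to 4 under Table 1, or 3 to 4 under the text of C.1.a, so the cut-off must be reconciled first.

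Optionally, if enrolment timing allows and the larger survey has no such item, add one baseline question on vaccine intention as a further covariate. The downsides are a small amendment, missing values for parents already enrolled (the current text already refers to a survey in summer 2020), and a gain that depends on how well stated intention predicts refusal.

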The following list of studies is intended to provide evidence of the rationale for the PIVOT with MI intervention and the study team's expertise in the methods proposed in the current application. Please also note that the study team has expertise in organizing and conducting provider focus groups to obtain feedback on vaccine materials and intervention design, as proposed in Aim 1.⁸¹⁻⁸³

C.1.a. Development and Evaluation of the Parent Attitudes about Childhood Vaccines Short Form (PACV-SF) Survey ([name], PI; [name], Co-I; [name], Co-I):

The PACV is a 15-item survey designed to identify VHPs that takes <5 minutes to complete and reads at the 6 – 7th grade level. We developed the PACV using a standard iterative process.⁸⁴ The PACV's validity was then evaluated in 2 separate studies and found to have both construct and predictive validity.^{17,18} [ENREF 69](#) Ongoing evaluations of the PACV support its validity in different geographic populations^{29,85,86} and clinical settings.⁸⁷ In collaboration with investigators at Texas Children's, we have also developed a Spanish version of the PACV using the 4-step WHO guidelines for translation of instruments.⁸⁸

[name] and [name] also conducted a secondary analysis of predictive validity data to identify a short form of the PACV (PACV-SF; Table 1). Different candidate item combinations and score thresholds were optimized on 4 criteria: 1) reflection of the major sub-domains of vaccine hesitancy; 2) specificity [to minimize false positives]; 3) sensitivity [to maximize true positives]; and 4) minimize the total number of items on the PACV-SF. Construct validity data was then used as a cross-validation sample to assess PACV-SF performance.

We found that hesitant responses on ≥ 3 of 4 items optimized our 4 criteria: it had an 85% (95% CI: 75, 92) sensitivity and 96% (95% CI: 94, 98) specificity in the original sample and 90% (95% CI: 79, 96) sensitivity and 95% (95% CI: 90, 98) specificity in the validation sample for identifying respondents with PACV scores ≥ 50 .

We concluded that the PACV-SF is valid for identifying VHPs and will be used to do so in the proposed study.

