C.6.g. Data Collection and Implementation: During the intervention period, all English- and Spanish-speaking parents of newborns will be screened with the PACV-SF prior to their initial visit at a participating practice by integrating the PACV-SF into standard practice workflow (see *C.6.e.1.*). The PACV-SF will also include demographic items that have been associated with under-immunization (birth order of their child, household income, marital status, parent self-designated race/ethnicity, gender, and number of children in their household)^{31,113-115} and be embedded in a larger survey to minimize ascertainment bias.

To assess intervention fidelity (Aim 2a), a study RA will approach by phone English-speaking VHPs attending intervention practices who answer affirmatively to an item on the PACV-SF asking for their permission to contact them to determine their interest in participating in a study of provider-parent communication at health supervision visits in which their child’s visit will be videotaped. We will describe the study generally to parents in order to minimize the chance that parents alter their behavior to meet observer expectations. We will approach VHPs continuously throughout the intervention period to obtain a collection of videotaped encounters at different time periods to assess whether there is a waning of fidelity over time. We have chosen videotaping because it captures aspects of nonverbal communication that are (a) not captured by audiotaping alone and are essential to our study of vaccine acceptance (e.g. head nodding) and (b) necessary to provide visual feedback to providers during the 12 month refresher session (see *C.6.f.*).¹¹⁶ For those VHPs who are interested (based on our past studies, we expect $>70\%$ will be interested [see *C.1.c.*]), the study RA will meet the parent at their child’s next health supervision visit to obtain their written informed consent. The child’s visit will then be videotaped using a video-recorder equipped with a wide-angle lens and positioned in a corner of the exam room near the ceiling, consistent with the methods we have used in preliminary studies (see *C.1.c.*). All videotaped visits will be transcribed. Parents will receive a \$25 gift card for participating.

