C.6.j. Analysis: We will conduct an intention-to-treat analysis. The patient will be the unit of analysis. We will examine baseline characteristics of parents in control and intervention arms using Pearson's χ^2 tests (or Fisher's exact tests) for categorical variables and t-tests for continuous variables to assess for any unbalanced confounders. Any unbalanced confounders will be controlled for as covariates in all subsequent regression analyses. We will also compare baseline characteristics between parents with and without missing data. We will apply sensitivity analysis and multiple imputations techniques to address missing data.

Given the nested structure of the data, we will apply mixed effects regression models to examine the effects of the intervention on our primary outcome while controlling for covariates and accounting for correlations due to clustering. Let y_{ijk} denote the percent days under-immunized for child k who receives care from provider j at clinic i , let T_{ijk} be the intervention indicator (0=control, 1=intervention) for the child, let X_{ijk} be the collection of covariates that includes potential confounders (at patient, provider, or practice levels), then a mixed model that accounts for this specific nesting data structure can be specified by

$$y_{ijk} = T_{ijk}\alpha + X_{ijk}\beta + Z_{ijk}^{(3)} u_i^{(3)} + Z_{ijk}^{(2)} u_{ij}^{(2)} + \epsilon_{ijk}, \quad (1)$$

for $k = 1, \dots, n_{ij}$ first-level observations (patient) nested within $j = 1, \dots, M_i$ second level groups (provider), which are nested within $i = 1, \dots, M$ third-level groups (practices). $Z_{ijk}^{(3)}$ and $Z_{ijk}^{(2)}$ are design matrices for the third- and second-level random effects. Further normality and independence assumptions will be placed on random effects and error terms if the outcome is continuous. The above model specification represents a multi-level linear mixed model. Parameter estimates will be obtained through restricted maximum likelihood estimation. Robust sandwich standard error estimates to account for the clustering will be used for inference. In the above model specification, the parameter α captures the expected difference between intervention and control arms and will be our focus of inference. For binary outcomes, the above model specification can be adapted to mixed effects logistic regression with similar estimation and inference techniques.¹¹⁸

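### The primary model names no covariate in advance, so adjustment for degree of hesitancy among VHPs (the PACV-SF item count, already collected) is permitted but not secured

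*Combined protocol and SAP*

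**What the plan says.** - **Population (C.6.c).** "VHPs, defined as those who have a positive PACV-SF (see C.1.a.), will constitute our primary study population". No other parent-level use of the score is described for the primary analysis.
- **Primary model (C.6.j).** The covariate term in model (1) is "the collection of covariates that includes potential confounders (at patient, provider, or practice levels"). No variable is named. The operative rule is that parents' baseline characteristics are compared between arms by chi-square, Fisher or t-tests, and confounders found unbalanced go into all later regressions.
- **Baseline data (C.6.g).** The form is completed before the first visit. Besides the hesitancy items it carries "demographic items that have been associated with under-immunization". Under C.6.e.1 study staff collect and score the forms, and this screening continues through the intervention.
- **The instrument (C.1.a).** The 15-item PACV was "found to have both construct and predictive validity". The four-item short form came from a secondary analysis of the predictive-validity data. The text of C.1.a calls it positive at 3 or more hesitant answers; Table 1 says 2 or more.
- **Practice level (C.6.e).** Percent of VHPs per practice, measured before the intervention period, is one of four balancing variables in the constrained randomization.
- **Power (C.6.k).** The target is "a decrease in under-immunization of 10 days", and "we need to enroll 600 VHP/newborn pairs total, with 300 per arm and 25 at each of the 24 study practices", for at least 90% power.

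**The concern.** Degree of hesitancy is a natural candidate to predict days under-immunized. For newborns there is also a direct link: the footnote to Table 1 says that item 1 then concerns only delay of the hepatitis B birth dose, and C.6.i counts hepatitis B doses in the outcome. So item 1 partly records outcome days accrued before any intervention visit, and the answer can still vary among parents who screen positive.

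The rule in C.6.j is a weak route to using this information. It does not list the item count. It relies on parent-level tests although practices are randomized. It leaves the covariate set unknown until the data are seen. It brings a variable in only when the arms differ, whereas a prognostic covariate improves precision whether or not they differ.

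The constrained randomization does not fill the gap. It balances how many parents are VHPs in each practice during a pre-study period, not how hesitant the VHPs enrolled afterwards are. At stake are a little precision and a fully specified primary model.

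**Working it through.** **1. Reproduce the stated power.** Inputs from C.6.k: alpha 0.05 (taken as two-sided), SD 20, ICC 0.02, 300 pairs per arm, 25 in each of 24 practices.

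- Effect on the outcome scale: C.6.k reports a mean of 26.2% and says of it, "This corresponds to an average of 37 days late per vaccine dose". Ten days is then 26.2 x 10/37 = 7.08 percentage points.
- Design effect: 1 + 24 x 0.02 = 1.48. SE = 20 x sqrt(2 x 1.48/300) = 1.99.
- Power: 94.6% by the normal approximation, 92.6% by a noncentral t with 22 df. Both meet the stated 90%.
- Check on the conversion: 12,000 parents at 10% prevalence give 1,200 pairs. At SD 25 and 7.08 points their power is 93.7% (design effect 1 + 49 x 0.02 = 1.98), in line with the plan. Setting 10 directly against SD 25 gives 98.1% with only 600 pairs, so the plan would not have needed 1,200.

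**2. Score levels left among positives.** At a cut-off of 3 or more, positives score 3 or 4 (two levels). At 2 or more, they score 2, 3 or 4 (three levels).

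**3. How mixed the positives are.** C.1.a gives sensitivity/specificity of 85/96% and 90/95% against a full PACV score of 50 or more, at the cut-off of 3. With the 10% prevalence of C.6.k:

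- 0.1 x 0.85 / (0.1 x 0.85 + 0.9 x 0.04) = 0.70
- 0.1 x 0.90 / (0.1 x 0.90 + 0.9 x 0.05) = 0.67

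So 67-70% of positives would be VHPs on the full survey. No accuracy is given at the cut-off of 2, so the figure does not carry over to it.

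**4. Plausible R2 (assumed).** The documents give no outcome difference by score. Suppose the score is 3 or 4, 20-50% score 4, and the two levels differ by 5-15 points. R2 = p(1-p) x difference^2 / SD^2 is then 0.01-0.14 at SD 20 and 0.005-0.06 at SD 29.8. A working range of 2-10% is used below.

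**5. Power with the covariate.** R2 is applied to the within-practice part only:

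SE^2 = 2 x SD^2 x [0.98 x (1 - R2)/300 + 0.02/12]

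| SD | R2 | SE | Power (normal) |
|---|---|---|---|
| 20 | 0 | 1.99 | 94.6% |
| 20 | 0.02 | 1.97 | 94.8% |
| 20 | 0.10 | 1.92 | 95.8% |
| 29.8 | 0 | 2.96 | 66.7% |
| 29.8 | 0.02 | 2.94 | 67.3% |
| 29.8 | 0.10 | 2.86 | 69.7% |

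The SE falls by 0.7-3.4%. SD 29.8 is the value observed in the preliminary data for six vaccines (C.6.k). If the covariate also explained the same share of between-practice variance, R2 of 0.10 would give 96.4% and 71.3%.

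**6. Chance imbalance.** With a 70/30 mix and the same design effect, the SE of the between-arm difference in share is sqrt(2 x 0.7 x 0.3/300 x 1.48) = 0.046. If the two groups differed by 10-20 points (assumed), a one-SE imbalance would move the unadjusted difference by 0.5-0.9 points. That is 0.23-0.46 of the SE of 1.99 in step 1, which already includes this variation.

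**The case against.** The case for leaving the plan alone is substantial.

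- **The model has room for the score.** The covariate term admits patient-level confounders, and the imbalance rule could bring the item count in. This stands. A reader might infer that the model excludes hesitancy, or that protection against imbalance is lost; the text supports neither. What remains is that adjustment depends on a test and on someone counting the score among the baseline characteristics.
- **Hesitancy is used elsewhere.** Percent of VHPs is a balancing variable (C.6.e) and a subgroup factor (C.7.d). So it would be wrong to say that the PACV-SF serves only as a yes/no gate; that is true only of its parent-level use in the primary analysis.
- **Prediction within positives is not shown.** Predictive validity is stated for the 15-item survey, and the short form was tuned as a classifier. No section shows that one more hesitant answer among positives means more days under-immunized. This stands, and it is why R2 is an assumption. The hepatitis B item makes some association plausible but does not size it.
- **Chance imbalance as a second harm.** A reader might add the 0.5-0.9 point shift to the precision loss as a bias. That would count it twice, because it is random variation already in the SE. It also concerns full-PACV status, which the trial does not measure and a short count captures only in part.
- **The benefit is small.** This stands too. Under the plan's SD the design already exceeds its target, and at SD 29.8 the covariate does not bring power to 90%.

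**Conclusion.** The point holds as a modest gap in prespecification. C.6.j permits adjustment for degree of hesitancy among VHPs but does not secure it, and neither the generic covariate term nor practice-level balancing does so in its place.

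For an assumed R2 of 2-10%, the gain at 600 pairs is about 0.3-1.2 points of power at SD 20 and 0.6-3.0 points at SD 29.8. This rests on a two-sided test, no loss to follow-up, the 7.08-point conversion, and an R2 that the documents do not give. The 67-70% figure applies only if the cut-off is 3 or more.

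A reader might infer that the sample size is wrong or that the estimate would be biased without the score. The documents support neither: the stated power reproduces with no covariate, and leaving out a baseline predictor costs precision. The change is worth making because it replaces a test-driven rule with a fixed model using data already in hand.

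**What to change.** 1. Reconcile the PACV-SF cut-off between the text of C.1.a (3 or more) and Table 1 (2 or more). This decides whether two or three score levels remain in the primary population.
2. In C.6.j, state that model (1) for the primary outcome includes the PACV-SF item count, as categories, as a fixed covariate regardless of any baseline comparison.
3. Report the model without it as a sensitivity analysis. The form is completed before the first visit but after practices are randomized, so the reader should see that the result does not hinge on it.

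The cost is one or two sentences in C.6.j and one or two parent-level degrees of freedom. No new data are needed, and the sample size in C.6.k need not change on this account.
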